3.4 Intervention and Control

3.4.1 Control

Participants in the control group received usual care by the village doctors.

Village doctors bear multiple responsibilities in practice. Their routine work

includes providing generalist care and implementing the National Basic Public Health Services Program. These public health services include vaccination, health education; child health management; maternal health care; elderly health management; traditional Chinese medicine; reporting of infectious diseases and public health emergencies; and management for hypertension, type 2 diabetes, psychosis, and tuberculosis. These can be considered as usual care in a broad sense.

3.4.2 Intervention

Participants in the intervention group received a village doctor-led tailored health management program based on mHealth technologies. The multifaceted strategy is involved with all tagetes of the American Heart Association's Life's Essential 8, and includes five components:

(1) Assessing risk factors to identify individualized intervention targets

At baseline survey, the research staff conducted standardized interview and measurements to collect detailed information about each participant's existing risk factors (i.e., hypertension, diabetes, dyslipidaemia, obesity, smoking, alcohol use, physical inactivity, unhealthy diet, sleep deprivation) and medication adherence. Village doctors then were empowered to use this information to guide tailored health promotion for each participant. Participants' risk portrait was updated based on the remeasurements at each follow-up visit.

(2) Setting gradual goals based on doctor-participant communication

In a shared decision-making process, each participant was engaged in an in-depth discussion with his/her village doctor on their risk portrait at baseline. After fully communication, they created a checklist of seven health promotion goals for blood pressure, blood glucose, and blood lipid control, as well as weight loss, smoking cessation, alcohol reduction, and daily step count. The coordinating centre established a principle for the formulation of health promotion goals. These goals were evaluated at each subsequent follow-up visit, and updated based on their accomplishment.

(3) Providing targeted health promotion short messages and videos

The coordinating centre organized a multidisciplinary team comprising cardiologists, psychologists, public health specialists, and patients to develop a pool of health education short videos for this study. These short videos, lasting less than three minutes for each, presented educational content on physical exercise, healthy eating, smoking cessation, alcohol reduction, healthy sleep, and medication adherence, which were tailored for individuals with various combinations of risk factors, based on the latest recommendations from CVD prevention guidelines and behavioural change techniques. Village doctors received push notifications about several new short videos through the SMARTER WeChat mini program every Monday, Wednesday, and Friday, and they browsed and forwarded the short videos on specific topics to local participants with relevant conditions. The coordinating centre tracked the participants' viewing statistics and provided feedback to the village doctors.

(4) Conducting health monitoring and providing periodical feedback

A smart band (HUAWEI Band 4, Huawei Technologies Co., Ltd., Dongguan, China) was provided to each participant in the intervention group to help monitor their health data, including step count, heart rate, and sleep patterns. These data were uploaded 2 to 3 times per week. The study also encouraged participants to their self-measured blood pressure and glucose levels monthly, by responding to text messages from the coordinating centre. Weekly health monitoring reports for each participant were automatically generated and sent to the village doctors to enhance communication with participants regarding their progress in risk mitigation.

(5) Motivating to reduce risk based on gamification

With an automatic algorithm, the participants were provided a report detailing their progress in achieving seven individualized risk mitigation targets at each during follow-up visits. This report was presented in a visual format, featuring a virtual golden egg to symbolize achieving the target and a virtual bomb to represent failing to meet the target. Based on the number of virtual golden eggs received, participants could redeem gifts from the village doctors in real life.

3.5 Outcome Measures

3.5.1 Primary Outcomes

Mean changes in the 10-year risk of ASCVD based on the China-PAR risk prediction model from baseline to 12 months.

3.5.2 Secondary Outcomes

(1) Mean changes in lifetime risk of ASCVD based on the China-PAR risk prediction model from baseline to 12 months;

(2) Mean changes in systolic blood pressure (SBP) and diastolic blood pressure (DBP) from baseline to 12 months;

(3) Mean changes in fasting blood glucose (FBG) from baseline to 12 months;

(4) Mean changes in non-HDL cholesterol (non-HDL-C) from baseline to 12 months;

(5) Changes in proportion of overweight and obesity from baseline to 12 months;

(6) Changes in proportion of daily smoking from baseline to 12 months;

(7) Changes in proportion of insufficient physical activity (<3000 MET-min/wk) from baseline to 12 months;

3.6 Outcome Evaluation

The information of study outcomes (for participants in both intervention and control groups) was collected at baseline and each follow-up visits at 3th month, 6th month, 9th month, and 12th month. All the data collection was conducted using standardized equipment and following uniform operational protocols. These data were collected in three ways: (1) standardized electronic questionnaire interview; (2) physical examination; (3) fingertip blood sample collection.

The primary outcome, 10-year risk of ASCVD, was calculated by the China-PAR prediction model based on age, sex, geographic region (northern/southern China), urbanity, waist circumference, systolic blood pressure (SBP), use of antihypertensive

medication, presence of diabetes, total cholesterol (TC), high-density lipoprotein cholesterol (HDL-C), smoking status, and family history of ASCVD.

Regarding assessment of the metabolic risk factors, to be more specific, blood pressure was measured twice on the right upper arm using a standard sphygmomanometer (Omron HEM-7121, Omron Corporation, Japan) after 5 minutes of rest in the sitting position. Blood glucose and blood lipid were tested by the rapid blood glucose analyser (BeneCheck BK6-20 M Multi-Monitoring System, Suzhou Pu Chun Tang Biotechnology, China) and the fast photochemical lipid analyser (CardioChek PA Analyzer; Polymer Technology Systems, USA), respectively. Body mass index (BMI) was calculated as body weight in kilograms divided by the squared value of height in meters, with obesity was defined as a BMI≥28.0 kg/m².

For assessment of lifestyle behaviours factors, smoking status (never, former, or current smokers) and frequency were inquired in the questionnaire. Daily smoking was defined as self-reported consuming tobacco products every day. Regarding physical activity, we asked the participants about the time they spent on four types of physical activity (occupational, commuting, domestic, and leisure-time) in details, and overall physical activity level was quantified by multiplying the metabolic equivalent tasks (METs) value for each by time spent on that per day. According to studies of the global burden of disease (GBD), an overall physical activity of less than 3000 METmin per week was considered as insufficient physical activity. Leisure-time activity, as the focused part that could be intervened in the trial, we asked the participants about typical types of leisure-time activity at different intensity (swimming/running/aerobic exercise/ rope skipping as vigorous- intensity activity; ball games/hiking/brisk walking/gymnastics/folk dancing/Tai-Chi or qigong as moderate-intensity activity), frequency, and exercise time per week. Participants performing <150 minutes of moderate-intensity aerobic activities or <75 minutes of vigorous-intensity aerobic activities per week will be considered as having insufficient leisure-time activity.

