3.3.2 Secondary Outcomes

(1) Mean changes in lifetime risk of ASCVD based on the China-PAR risk prediction model from baseline to 12 months;

(2) Mean changes in systolic blood pressure (SBP) and diastolic blood pressure (DBP)

from baseline to 12 months;

(3) Mean changes in fasting blood glucose (FBG) from baseline to 12 months;

(4) Mean changes in non-HDL cholesterol (non-HDL-C) from baseline to 12 months;

(5) Changes in proportion of overweight and obesity from baseline to 12 months;

(6) Changes in proportion of daily smoking from baseline to 12 months;

(7) Changes in proportion of insufficient physical activity (<3000 MET-min/wk) from baseline to 12 months;

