physical activity (occupational, commuting, domestic, and leisure-time) in details, and overall physical activity level is quantified by multiplying the metabolic equivalent tasks (METs) value for each by time spent on that per day. According to studies of the global burden of disease (GBD), an overall physical activity of less than 3000 METmin per week is considered as insufficient physical activity. Leisure-time activity, as the focused part that could be intervened in the trial, we will ask the participants about typical types of leisure-time activity at different intensity (swimming/running/aerobic exercise/ rope skipping as vigorous- intensity activity; ball games/hiking/brisk walking/gymnastics/folk dancing/Tai-Chi or qigong as moderate-intensity activity), frequency, and exercise time per week. Participants performing<150 minutes of moderate-intensity aerobic activities or <75 minutes of vigorous-intensity aerobic activities per week will be considered as having insufficient leisure-time activity.

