

TABLES

Table 2. Cardiovascular	risk factors to	be assessed in t	the SMARTER study
	11511 100001 5 00		

Risk factors	Indicators	Warning criteria
10-year risk of ASCVD	Risk (value)	≥10%
	Risk (stratification)	High-risk
1. Hypertension	SBP	≥130 mmHg
	DBP	≥80 mmHg
2. Diabetes	FBG	≥6.1 mmol/L
3. Dyslipidaemia	TC	\geq 5.2 mmol/L
	Non-HDL-C	\geq 3.4 mmol/L
4. Obesity	BMI	Overweight: $\geq 24 \text{ kg/m}^2$, Obesity: $\geq 28 \text{ kg/m}^2$
	Bodyweight	According to the BMI criteria
	Waist circumstance	Males: ≥90 cm, Females: ≥85 cm
5. Smoking	Daily smoking amount	>0
	Heaviness of Smoking Index (HSI)	Heavy dependence
6. Alcohol use	Daily consumption of pure alcohol	≥15g (on average)
7. Physical activity	Total physical activity	<3000 MET-min/wk
	Exercise intensity	No exercise
	Weekly exercise time	Moderate-intensity aerobic activities<150 minutes, or vigorous-intensity aerobic activities<75 minutes
8. Unhealthy diet	Fruit	Less than everyday
	Fresh vegetables	Less than everyday
	Whole grains	Less than everyday
	Bean and bean food	Less than four days per week
	Red meat	Everyday
9. Sleep deprivation	Sleep duration	<6 hours/day (on average)
10. Medication adherence	Self-reported adherence	Intermittent or absent use of medications

Risk factors	Targets	Principles
Hypertension	SBP/DBP	Age<80: <130/80 mmHg; Age≥80: <150/90 mmHg (recommended; allow for adjustment according to the circumstances)
Diabetes	FBG	Participants without a diagnosis of DM: <6.1 mmol/L; DM patients: <7.0 mmol/L
Dyslipidaemia	Non-HDL-C	Age<75, no diagnosis of DM: <3.4 mmol/L; Age<75, DM patients: <2.6 mmol/L; Age ≥75: lipid lowering target should be set under guidance of the physicians in higher-level hospitals

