6.4 Analysis of Secondary Outcomes

The secondary outcomes included mean changes in the levels of lifetime risk of ASCVD based on the China-PAR model, SBP, DBP, FBG, and non-HDL-C, as well as changes in the proportions of obesity, daily smoking, and insufficient physical activity, from baseline to the 12 months. The assessment of secondary outcomes of continuous variables will be analysed using linear mixed effects models, same as the analysis method of primary outcome, and the categorical variables will be analysed using the generalised linear mixed effects models. Villages will be adjusted in the

models as a random effect. The net differences between the two groups were assessed by the models, with multivariable adjustment by baseline covariates including age, sex, education, occupation, annual household income, marital status, and social medical insurance.

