Insufficient leisure-time activity (<150/75 min/wk)	1541 (68.6%)	1040 (46.3%)	-22.3% (-24.7% to -19.9%)	1420 (64.9%)	1372 (62.7%)	-2.2% (-4.5% to 0.1%)	0.38 (0.24 to 0.59)	< 0.001

* Data were mean (SD), n (%), mean (95%CI) or OR (95%CI) unless otherwise stated.

All net group difference was adjusted for clustering effects by villages (as random effect), four minimisation factors, age, sex, education, occupation, annual household income, marriage status, social medical insurance, and baseline level of the outcome.

	Interv	ention (n=2246)	Co	ntrol (n=2188)	Net Group Difference	D l	D :
Subgroup	Number	Changes (95%CI)	Number	Changes (95%CI)	(95%CI)	P value	P-inter
Age, year							0.73
<60	1352	-7.0 (-7.3 to -6.6)	1301	-5.2 (-5.6 to -4.9)	-1.86 (-2.57 to -1.16)	< 0.001	
≥60	894	-5.2 (-5.6 to -4.8)	887	-2.7 (-3.1 to -2.3)	-1.82 (-2.63 to -1.01)	< 0.001	
Sex							0.03
Male	1130	-7.2 (-7.6 to -6.7)	1062	-4.6 (-5.0 to -4.2)	-2.20 (-3.05 to -1.36)	< 0.001	
Female	1116	-5.4 (-5.7 to -5.1)	1126	-3.8 (-4.1 to -3.5)	-1.55 (-2.20 to -0.90)	< 0.001	
Education							0.74
Below high school	1755	-6.0 (-6.3 to -5.7)	1749	-4.1 (-4.4 to -3.9)	-1.83 (-2.54 to -1.12)	< 0.001	
High school and above	491	-7.3 (-7.9 to -6.7)	439	-4.4 (-5.0 to -3.7)	-2.11 (-3.03 to -1.20)	< 0.001	
Occupation							0.03
Farmer	1535	-6.1 (-6.4 to -5.8)	1465	-4.4 (-4.7 to -4.0)	-1.63 (-2.41 to -0.85)	< 0.001	
Non-farmer	711	-6.6 (-7.1 to -6.1)	723	-3.8 (-4.3 to -3.4)	-2.60 (-3.37 to -1.83)	< 0.001	
Annual household income, yuan							0.02
<10 000	358	-5.1 (-5.8 to -4.5)	347	-2.4 (-3.1 to -1.8)	-2.76 (-3.90 to -1.63)	< 0.001	
≥10 000	1888	-6.5 (-6.8 to -6.2)	1841	-4.5 (-4.8 to -4.2)	-1.72 (-2.40 to -1.03)	< 0.001	
10-year risk of ASCVD, %							< 0.001
<16	1128	-3.5 (-3.7 to -3.3)	1128	-2.3 (-2.6 to -2.0)	-1.14 (-1.76 to -0.52)	< 0.001	
≥16	1118	-9.0 (-9.5 to -8.6)	1060	-6.2 (-6.6 to -5.8)	-2.57 (-3.42 to -1.72)	< 0.001	

 Table S6 (b). Subgroup results of the primary outcome (sensitivity analysis: excluding participants with MACEs)

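### The leisure-time activity rule joins its thresholds with 'or', so read literally it requires both, and this defined but unlisted outcome sits among the secondary outcomes in Table S6(a)

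*Combined protocol and SAP*

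**What the plan says.** The rule appears three times with the same connective. SAP 3.6 (Outcome Evaluation) classes as insufficient "Participants performing <150 minutes of moderate-intensity aerobic activities or <75 minutes of vigorous-intensity aerobic activities per week". Protocol 5.1 (Data Collection) says the same of those with less than 150 "minutes of moderate-intensity aerobic activities or <75 minutes of vigorous-intensity aerobic activities per week will be considered as having insufficient leisure-time activity". Protocol Table 2 uses it as a warning criterion for weekly exercise time: "Moderate-intensity aerobic activities<150 minutes, or vigorous-intensity aerobic activities<75 minutes".

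The outcome lists do not include leisure-time activity. The only activity item in protocol 3.3.2 and SAP 3.5.2 is "Changes in proportion of insufficient physical activity (<3000 MET-min/wk) from baseline to 12 months". SAP 6.4 names the binary secondary outcomes as "changes in the proportions of obesity, daily smoking, and insufficient physical activity". The exploratory list in protocol 3.3.3 has two items, medication adherence and MACEs.

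Appendix 3 Table S6(a) nevertheless has a row labelled "Insufficient leisure-time activity (<150/75 min/wk" in its secondary-outcomes block, separate from the row for total activity below 3000 MET-min/wk. The net group difference is printed as "0.38 (0.24 to 0.59", with P<0.001. The code in Appendix 4 tabulates LTPA0 and LTPA4 but does not show how they were derived.

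**The concern.** There are two separate problems.

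The first is the rule. The usual way to combine two alternative thresholds is that reaching either one is enough. The opposite of that is falling short on both. The documents define insufficiency as falling short on either, which is the opposite of reaching both. An analyst who follows the text would class as insufficient a participant who walks briskly for 300 minutes a week and does no vigorous exercise. The same goes for one who runs for 150 minutes and does nothing moderate. The intervention sets daily step goals, so participants who do only moderate activity matter here.

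The second is status. Among the binary rows of Table S6(a) this one has the odds ratio furthest from 1: 0.38, against 0.63 for total activity, 0.61 for daily smoking and 0.83 for obesity. A self-reported measure in an open-label trial is shown as a secondary outcome although no list names it as one.

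**Working it through.** **1. What the written rule does.** Let M and V be weekly moderate and vigorous minutes. The table compares the written rule (M<150 or V<75) with the direct negation of reaching either threshold (M<150 and V<75).

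| M | V | Written rule | Direct negation |
|---|---|---|---|
| 0 | 0 | insufficient | insufficient |
| 149 | 74 | insufficient | insufficient |
| 150 | 0 | insufficient | sufficient |
| 300 | 0 | insufficient | sufficient |
| 300 | 74 | insufficient | sufficient |
| 0 | 150 | insufficient | sufficient |
| 150 | 75 | sufficient | sufficient |

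The rules differ for exactly one group: people who meet one threshold and not the other. Under the written rule, being sufficient takes at least 150 + 75 = 225 minutes a week, with both parts met.

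**2. What the reported figures imply.** The counts are from Table S6(a), and sufficient = total − insufficient.

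| Group and time | Insufficient | Sufficient |
|---|---|---|
| Intervention, baseline | 1541/2246 = 68.6% | 705 = 31.4% |
| Intervention, 12 months | 1040/2246 = 46.3% | 1206 = 53.7% |
| Control, baseline | 1420/2188 = 64.9% | 768 = 35.1% |
| Control, 12 months | 1372/2188 = 62.7% | 816 = 37.3% |

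The printed percentages and changes reproduce: 46.3 − 68.6 = −22.3 points and 62.7 − 64.9 = −2.2 points. Under the literal rule all 1206 sufficient participants in the intervention group at 12 months would have done at least 75 vigorous minutes on top of at least 150 moderate minutes. About 40% of the cohort in these tables is aged 60 or over (Table S6(b): 894/2246 = 39.8% and 887/2188 = 40.5%). That is a reason to check the coding. It does not settle it, because the documents give no distribution of M or V. For the same reason, the counts and OR under another rule cannot be computed.

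**3. Is the P value fragile?** From the printed OR and interval, by a Wald test:

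- SE = [ln(0.59) − ln(0.24)] / (2 × 1.96) = 0.229
- z = ln(0.38) / 0.229 = −4.22
- P ≈ 2.5 × 10⁻⁵ (about 1 × 10⁻⁵ to 6 × 10⁻⁵ allowing for rounding)

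This agrees with the printed P<0.001. SAP 5.1 gives no multiplicity rule, but a Bonferroni limit over 8 to 10 outcomes is 0.05/8 = 0.00625 to 0.05/10 = 0.005, which this P value passes easily. The adjusted mixed model cannot be refitted without participant data.

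**4. Effect on the primary outcome.** None. The China-PAR inputs listed in SAP 3.6 do not include physical activity.

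**The case against.** **The rule has a natural reading by type of exercise.** It could mean under 150 minutes for those who exercise moderately, or under 75 for those who exercise vigorously. The row label with its slash fits that, and all three statements of the rule agree with one another. This may well be the intent, but it is not what the sentence says. It also gives two answers for someone who does both types, for example 200 moderate and 30 vigorous minutes.

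**No harm is demonstrated.** A reader might infer that LTPA0 and LTPA4 were miscoded and that the OR of 0.38 is wrong. The documents do not support this. If the variables already follow the either-threshold rule, nobody was misclassified and the result stands. The view that 31% to 54% is too many to meet both thresholds is a judgement without a figure behind it. This objection holds, so the point is limited to the written rule and its traceability.

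**The measure was planned.** A reader might infer that the outcome was invented after the data were seen. That is not supported either. Protocol 5.1 and SAP 3.6 both define it and single out leisure-time activity as the component the intervention could change. SAP 3.1 describes the secondary outcomes broadly as changes in metabolic and lifestyle risk factors, and SAP 6.4 names insufficient physical activity without a cut-off. However, SAP 3.5.2 fixes that item at 3000 MET-min/wk, and Table S6(a) shows the two measures as separate rows. SAP 6.6 allows assessments to be added by amendment, but the documents show none for this outcome. The accurate description is that it was defined but not listed.

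**The row comes from a supplementary sensitivity table.** This is true. The main results table is not in the documents, so its labelling there is unknown.

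**Self-report and open label are not special to this row.** This is also true. Daily smoking and total activity share both features and are listed secondary outcomes.

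**Conclusion.** The concern holds on two limited counts. First, the rule in protocol 5.1 and SAP 3.6 is wrong as worded: taken literally, it classes everyone who meets only one threshold as insufficient. It would be too broad to say that everyone meeting the moderate threshold is misclassified, since those who also reach 75 vigorous minutes are sufficient. The number affected cannot be derived from the documents. Second, an outcome that was defined in advance but is absent from every outcome list is presented as secondary in Table S6(a).

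This rests on the literal wording, on the counts in a table that excludes participants with MACEs, and on the absence of any derivation of LTPA0 and LTPA4. The finding concerns definition and status, not the strength of the statistical evidence. It should be corrected, but it does not touch the trial's main conclusion.

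**What to change.** 1. State how LTPA0 and LTPA4 were derived.
2. Correct protocol 5.1 and SAP 3.6 so that insufficient means below 150 moderate and below 75 vigorous minutes per week. Results already exist, so record this as a documented correction, in line with the requirement in SAP section 1 to describe and justify deviations.
3. Rerun the row only if the coding followed the literal *or*.
4. Report any combined-minutes rule only as a sensitivity analysis, because it is not equivalent. With 100 moderate and 50 vigorous minutes, a rule that counts vigorous minutes twice gives 100 + 2 × 50 = 200, which is sufficient against 150. The corrected rule classes the same person as insufficient.
5. Label the row in Table S6(a) as *defined in the protocol and SAP but not listed as a secondary outcome; exploratory*, and use the same label wherever else the outcome is reported.
6. Reconcile the matching wording in protocol Table 2 with the other two places.

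The cost is one sentence in each document, a check of two variables, a table footnote and possibly one rerun. The downside is that a striking result loses secondary status.

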3. SAMPLE SIZE

The sample size for the proposed trial was calculated based on the primary outcome. At the time of the study design, we calculated a minimum sample size of 4200 participants in 120 villages (60 villages in each comparison group, and 35 participants in each village), which would provide a statistical power of 90% with a two-sided significance level of 0.05 to detect an 1.0% absolute difference in the 12-month change of 10-year risk of ASCVD between the intervention and control groups. The calculation assumed a standard deviation (SD) of 6.0% for both the intervention and control groups at baseline, an intra-cluster correlation coefficient (ICC) of 0.04, and allowed a loss of follow-up of 10%.

To compensate for the risk of entire-village withdrawing, the study screened more villages at enrolment. At last, a total of 4533 participants from 127 villages were included. With an actual ICC of 0.06, the statistical power finally achieved was 88%.

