Control	(992/2212)	(1295/2197)	(1395/2207)	(1480/2203)	(1556/2200)	P<0.001*
(Mean change	e) Interventior	1: 35.6% (33.5	% to 37.8%),	Control: 25.9%	6 (23.8% to 27.9	%)

Table S5. Exploratory Outcome: Medication adherence

* Medication adherence was defined as taking the full dose of prescribed medications ≥6 days per week among all participants with hypertension, diabetes, or dyslipidaemia. The net group difference was adjusted for clustering effects by villages (as random effect), four minimisation factors, age, sex, education, occupation, annual household income, marriage status, social medical insurance, and baseline level of the outcome.

Fig S4. Exploratory Outcome: MACEs

* The HR and 95%CI of MACEs were estimated by Cox frailty model with adjustment of clustering effects by villages (as random effect), four minimisation factors, age, sex, education, occupation, annual household income, marriage status, and social medical insurance.

	Intervention (n=2246)				Control (n=2	2188)	Net Group Difference	Darahar
	Baseline	12-month	Change (95%CI)	Baseline	12-month	Change (95%CI)	(95%CI)	P value
Primary outcome								
10-year risk of ASCVD, %	18.0 (7.1)	11.7 (5.8)	-6.3 (-6.5 to -6.0)	17.7 (6.8)	13.5 (6.9)	-4.2 (-4.5 to -3.9)	-1.88 (-2.57 to -1.19)	< 0.001
Secondary outcomes								
Lifetime risk of ASCVD, % *	49.9 (15.4)	34.0 (12.7)	-15.9 (-16.4 to -15.3)	49.4 (15.8)	38.4 (14.8)	-11.0 (-11.5 to -10.4)	-4.59 (-6.23 to -2.96)	< 0.001
Systolic blood pressure, mmHg	157.7 (16.2)	134.4 (12.1)	-23.2 (-23.9 to -22.5)	157.0 (16.1)	141.9 (16.1)	-15.0 (-15.8 to -14.3)	-7.70 (-9.38 to -6.02)	< 0.001
Diastolic blood pressure, mmHg	93.4 (11.0)	82.5 (8.0)	-10.9 (-11.3 to -10.4)	92.6 (10.7)	85.8 (9.8)	-6.8 (-7.2 to -6.4)	-3.63 (-4.70 to -2.55)	< 0.001
Fasting blood glucose, mmol/L	7.2 (2.7)	6.3 (1.6)	-0.9 (-1.0 to -0.8)	7.1 (2.5)	6.6 (1.8)	-0.5 (-0.6 to -0.4)	-0.29 (-0.51 to -0.07)	0.009
Non-HDL-C, mmol/L	3.4 (1.2)	3.0 (1.1)	-0.4 (-0.4 to -0.3)	3.4 (1.3)	3.1 (1.1)	-0.3 (-0.4 to -0.3)	-0.06 (-0.19 to 0.08)	0.43
Obesity	869 (38.7%)	784 (34.9%)	-3.8% (-5.0% to -2.6%)	842 (38.5%)	792 (36.2%)	-2.3% (-3.5% to -1.1%)	0.83 (0.65 to 1.05)	0.13
Daily smoking	515 (22.9%)	449 (20.0%)	-2.9% (-4.0% to -1.9%)	473 (21.6%)	462 (21.1%)	-0.5% (-1.5% to 0.4%)	0.61 (0.43 to 0.85)	0.004
Insufficient physical activity	315 (14.0%)	247 (11.0%)	-3.0% (-4.6% to -1.5%)	309 (14.1%)	337 (15.4%)	1.3% (-0.3% to 2.8%)	0.63 (0.42 to 0.94)	0.03
(<3000 MET-min/wk)								

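### The 88% reported as achieved power appears to keep the planning SD; the one reported confidence interval for the overall primary comparison implies about 81%

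*Combined protocol and SAP*

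**What the plan says.** The plan in SAP section 3 (Sample Size), repeated in protocol section 4.1, has these parts:

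- Target: "detect an 1.0% absolute difference in the 12-month change of 10-year risk of ASCVD", with 90% power and "a two-sided significance level of 0.05".
- Size: a "minimum sample size of 4200 participants in 120 villages", 35 per village.
- Variability: "The calculation assumed a standard deviation (SD) of 6.0% for both the intervention and control groups at baseline".
- Clustering and loss: "an intra-cluster correlation coefficient (ICC) of 0.04"; the plan also "allowed a loss of follow-up of 10"%.

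The SAP then reports that 4533 participants in 127 villages were included, and adds: "With an actual ICC of 0.06, the statistical power finally achieved was 88"%. It gives no SD, analysed number or loss for that last figure, and does not say what kind of ICC it is (of the raw risk, of the change, or of the model residuals).

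The observed data are in Appendix 3, Table S6(a), which leaves out participants with MACEs (2246 intervention, 2188 control). For 10-year risk the SDs are 7.1 and 6.8 at baseline and 5.8 and 6.9 at 12 months. The adjusted net difference is minus "1.88 (-2.57 to -1.19").

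**The concern.** The words chosen for the 88% present it as power that the trial realised. The ICC, participants and villages behind it are realised values, but the only SD the section names is the planning value of 6.0, and the observed baseline SDs are larger. If the SD was carried over, the sentence joins observed and assumed inputs and calls the result achieved.

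What is at stake is one descriptive figure. A reader would take it that the trial fell 2 points short of its 90% target for a 1.0-point difference, whereas its reported precision suggests about 9 points. No sample size, analysis or decision rule depends on the sentence.

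**Working it through.** **Formula.** With N analysed participants, k villages and m = N/k, the design effect is DEFF = 1 + (m − 1) × ICC. The standard error is SE = SD × √(2 × DEFF / (N/2)). Power for 1.0 point is Φ(1.0/SE − 1.96).

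**1. The planned 90%.** SD 6.0, ICC 0.04, 4200 less 10% = 3780.
- m = 3780/120 = 31.5: DEFF = 2.22, SE = 0.291, power 93.0%.
- m kept at 35: DEFF = 2.36, SE = 0.300, power 91.5%.

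The planned 90% is met either way.

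**2. The stated 88%.** SD 6.0, ICC 0.06, 127 villages.

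| Analysed N | m | DEFF | SE | Power |
|---|---|---|---|---|
| 4533 less 10% = 4079.7 | 32.1 | 2.867 | 0.318 | 88.2% |
| 4434 | 34.9 | 3.035 | 0.314 | 89.0% |
| 4533 | 35.7 | 3.082 | 0.313 | 89.2% |

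So 88–89% follows from the realised ICC, participants and villages with an SD of 6.0. That 6.0 was kept is an inference from this match.

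**3. Power from the reported precision.** The CI half-width is (2.57 − 1.19)/2 = 0.69. Rounding of the bounds allows 0.685 to 0.695. Take a critical value of 1.96 (normal) or 1.98 (t with about 110 degrees of freedom).
- Smallest SE: 0.685/1.98 = 0.346, power Φ(1/0.346 − 1.96) = 82.4%.
- Central: 0.69/1.96 = 0.352, power 81.1%; 0.69/1.98 = 0.348, power 81.9%.
- Largest SE: 0.695/1.96 = 0.355, power 80.5%.

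Power of 88% needs SE = 1/(1.96 + 1.175) = 0.319, which no rounding of the CI allows. This route needs no assumption about the SD or the ICC.

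**4. Observed SDs in the formula, ICC 0.06.** The baseline and 12-month SDs are pooled over the two arms in Table S6(a). The SD of change is recovered from the arm CIs: intervention 0.5/(2 × 1.96) × √2246 = 6.0, control 0.6/(2 × 1.96) × √2188 = 7.2.

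| SD used | Pooled value | 4533 less 10% | 4434 | 4533 |
|---|---|---|---|---|
| Baseline | 6.95 | 77.4% | 78.5% | 78.8% |
| Change, from arm CIs | 6.62 | 81.3% | 82.3% | 82.6% |
| 12-month | 6.37 | 84.2% | 85.1% | 85.4% |

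The change row is weakly determined. The CIs are printed to one decimal, which allows about 4.8–7.2 (intervention) and 6.0–8.4 (control). Rebuilding the SD of change from the subgroup CIs in Table S6(b) centres near 6.4, or about 84–85%.

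**5. Can the cause be identified?** With 4434 participants, SE 0.352 and SD 6.0, DEFF = (0.352/6.0)² × 2217/2 = 3.81 and ICC = 2.81/33.9 = 0.083. With ICC 0.06 instead, the same SE needs an SD of 0.352/√(2 × 3.035/2217) = 6.7. Either pair gives the same SE, so the CI cannot tell them apart.

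**The case against.** The strongest reply has five parts.

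- **The SD may not be the fault.** The reported SE comes from a model that adjusts for baseline risk, the minimisation factors and other covariates (Table S6(a) footnote, Appendix 4 code). If adjustment brought the residual SD to about 5.5, ICC 0.06 would give about 93% power, and an SE near 0.35 would need a residual ICC of about 0.10. This stands as a point about cause. It does not rescue 88%, because the SE is about 0.35 whatever produced it.
- **The low end rests on the wrong SD.** The outcome is a change, so the 77–79% from the baseline SD is only the like-for-like replacement for the SAP's own label. A reader might infer that true power was 77%, or 13 points under target. The documents do not support that: the 12-month and subgroup-derived SDs give 84–85%, and rounding does not exclude an SD of change near 6.0.
- **The baseline SD may have been a fair stand-in.** With equal variances the SD of change equals the baseline SD at a correlation of 0.5, and is smaller above that. The arm figures suggest a correlation roughly in that region. The SAP states none, but this is no ground for calling the planned 90% wrong.
- **The analysis set differs.** All observed figures exclude participants with MACEs, and the main results table is not in the documents. This stands as a caveat. But 4434 is 98% of 4533, and bringing the SE from about 0.35 to 0.319 would need a fall of about 9% from adding back about 2% of participants, which is implausible.
- **Post hoc power adds little.** Agreed. The difference of −1.88 has a CI that excludes zero and lies wholly beyond 1.0 point. That is a reason to drop the sentence, not to keep an inaccurate figure.

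**Conclusion.** The point holds and is minor. The 88% matches realised clustering and numbers combined with what appears to be the planning SD. The trial's reported precision gives about 81% (80.5–82.4%) for the 1.0-point design difference, roughly 7 points lower. This rests on reading the SE from a CI printed to two decimals, and on the MACE-excluded set being close to the primary analysis set.

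A reader might go further and infer that only the ICC was updated, or that the SD was shown to be too small. The section also moves to the realised participants and villages, and the documents cannot separate a larger SD from a larger residual ICC. Nor do the figures cast doubt on the planned 90% or on the reported treatment effect.

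**What to change.** Preferred: delete the sentence on achieved power in SAP section 3 and let the confidence interval show the precision.

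Alternative: restate it as about 81% power for a 1.0-point difference, based on the primary model's observed standard error. Recompute that on the full primary analysis set before printing it.

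If a formula-based figure is kept, state the SD of change (or the residual SD), the analysed number, the loss and the type of ICC, all taken from the same data and model.

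The cost is one sentence and, if a figure is kept, a less favourable one. No participants, data or analyses of outcome are affected.
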